	12. Is on another antiviral or is participating in a clinical trial for the treatment of COVID-19.							
	13. Subject is on ventilator at the time of study entry.							
	14. Is deemed by the Investigator to be ineligible for any reason.							
Treatment Regimen for Favipiravir (Standard dose)	 Favipiravir tablets will be administered orally. If necessary, a slurry may be administered by nasogastric tube. The regimen begins with loading doses of 1800 mg BID on Day 1 (the first 24 hours of treatment at t =0 and t = 12 hours) then maintenance dosing of 1000 mg BID from Day 2 (beginning 24 hours after the start of therapy). Patients with Child-Pugh liver impairment of grade A will have their maintenance dose decreased to 800 mg BID. The total duration of treatment is expected to be 14 days. The dose regimen may be altered, after consultation between the treating physician and the Sponsor, depending on the clinical condition of the patient. 							
Duration of Study Participation	Subjects will participate in the study for up to 60 days: 14 days treatment (or as discussed with the Sponsor) and 46 days follow up.							
Statistical Methods	This study is intended to be exploratory. Based upon available data, two-arm study of approximately 50 total subjects will be sufficient provide reasonable assurance that the endpoints chosen for confirmatory trial will elucidate treatment differences between favipiravir and a control. Statistical significance testing will be used to assess the relative strength of evidence of the primary and secondary endpoints.							
	Randomization will be stratified by:Site							
	• Severity of illness at enrollment:							

o Critical disease:

- Requires supplemental oxygen delivered by non-rebreather mask or high-flow cannula, OR
- Use of invasive or non-invasive ventilation, OR
- Requiring treatment in an intensive care unit, use of vasopressors, extracorporeal life support.
- Severe disease:
 - Evidence of pneumonia on chest x-ray or CT scan, or chest auscultation (rales, crackles), OR
 - SpO2 ≤ 93% on room air OR PaO2/FiO2 < 300 mmHg, OR
 - Requires supplemental oxygen by nasal canula, simple face mask, or other similar oxygen delivery device.
- Mild-moderate disease: SpO2 > 94% and respiratory rate < 24 breaths/min without supplemental oxygen
- There is no planned interim analysis.

Individual Stopping Rule

A subject should be removed from favipiravir treatment if one of the following criteria is met:

- AST or ALT $> 8 \times ULN$
- ALT or AST $> 3 \times ULN$ AND total bilirubin $> 2 \times ULN$
- AST or ALT > 3 × ULN AND patient has right upper quadrant pain or eosinophilia
- Uric acid > 20 mg/dL

Study Measurements: Efficacy, Safety and PK

Primary Efficacy Measurement:

Presence of virus in the nasopharyngeal and oropharyngeal samples taken on Days 1, 3, 8, 11, 15 and 29 (if hospitalized and when able to return to clinic after discharge). Swabs will also be obtained on day of discharge from hospital if discharge occurs before Day 15.

Secondary Measurements (Efficacy, Safety and PK):

- 1. Clinical improvement of hospitalized subjects with COVID-19 receiving either favipiravir + SOC or SOC alone as defined by the following study-specific 6-point ordinal scale at Day 15
 - a. Not hospitalized
 - b. Hospitalized, not requiring supplemental oxygen
 - c. Hospitalized, requiring supplemental oxygen
 - d. Hospitalized, on non-invasive ventilation or high flow oxygen devices
 - e. Hospitalized, on invasive mechanical ventilation or ECMO
 - f Death
- 2. Status on the 6-point ordinal scale assessed daily while hospitalized and at each outpatient visit until Day 60.
- 3. NEWS2 assessed daily while hospitalized and at each outpatient visit until Day 60.

- 4. Patient status assessed daily while hospitalized and at each outpatient visit until Day 60 via Study-specific Symptom Status and the ECOG Performance Status questionnaires (see Appendix A).
- 5. Duration of supplemental oxygen (if applicable).
- 6. Duration of mechanical ventilation (if applicable).
- 7. Duration of hospitalization.
- 8. Date and cause of death (if applicable).
- 9. Safety as assessed by:
 - a. Observed and reported adverse events.
 - b. Hematology and chemistry laboratories on Days 1; 3, 8, 11, 15 and 29 (if hospitalized and when able to return to clinic after discharge)
 - c. Physical Examination at screening, Day 15 and Day 29.
 - d. Vital signs daily while hospitalized and at each outpatient visit until Day 60
- 10. Qualitative and quantitative PCR and TCID50 in nasopharyngeal and oropharyngeal swabs on Days 1 (pre-dose); 3, 8, 11, 15 and 29 (if hospitalized and when able to return to clinic after discharge). Swabs will also be obtained on day of discharge from hospital if discharge occurs before Day 15.
- 11. Blood for determination of antibodies to SARS-CoV-2 will be obtained on Days 1, 15 and 29 (if hospitalized and when able to return to clinic after discharge).
- 12. Blood 6.0 ml for PK in patients randomized to favipiravir is obtained pre-dose (within 30 minutes prior to dosing) and post-dose (45 to 75 minutes following dosing) on Day 1 and trough levels on Days 2, 8 and the last day of favipiravir treatment (Day 14 unless subject leaves the study before completing treatment) and peak levels on Days 3 and 11 post-dosing.

To gather these measurements – subjects will undergo 9 planned venipunctures

2 INTRODUCTION

2.1 Background Information

Favipiravir, a small molecule, is a novel anti-viral agent discovered by FUJIFILM Toyama Chemical Co., Ltd. It is a broad-spectrum antiviral that includes activity against all RNA virus families tested, including rabies, Ebola, Lassa, and coronaviruses. It has been in clinical trials for influenza, Severe Fever with Thrombocytopenia virus, Ebola, and has been used under compassionate release for Ebola, rabies, Lassa fever, norovirus and COVID-19. As of the date of this protocol, three Chinese studies exploring its use against COVID-19 have been posted to the Chinese Clinical Trial Registry website (http://www.chictr.org.cn/showprojen.aspx?proj=49015 http://www.chictr.org.cn/showprojen.aspx?proj=49013).

Results from one study have been reported as demonstrating that viral PCR titers fall faster in patients treated with favipiravir plus interferon as compared with patients treated with interferon plus lopinavir/ritonavir.

Host cellular enzymes convert favipiravir to T-705 ribosyl triphosphate (T-705RTP), which selectively inhibits viral RNA polymerase. Based on its potent and selective inhibitory activities against a broad spectrum of influenza A, B, and C viruses, including strains poorly susceptible to amantadine hydrochloride or oseltamivir phosphate, favipiravir has been approved in Japan for the treatment of uncomplicated influenza, when currently available anti-influenza medications are not sufficient.

Favipiravir has been tested against the novel corona virus COVID-19, which causes disease ranging from mild, cold-like symptoms to acute respiratory failure and death. Epidemiologic studies are underway to determine whether individuals can be asymptomatic and transmit disease. There is currently no available treatment for COVID-19.

2.2 Preclinical and In Vitro Experiences

Preclinical and animal studies indicate that favipiravir is effective against RNA viruses causing a variety of disorders.

Preclinical and animal studies show no direct suppression of white blood cell types or immunosuppression by favipiravir. This contrasts with strong immunosuppressive effects of ribavirin and other antiviral agents.

Genotoxicity studies indicate that favipiravir does not pose a clinical genotoxic risk, however, based on the results of embryo-fetal toxicity studies, favipiravir is not recommended for use in pregnant females, those who may become pregnant, or those who are nursing. A human testicular toxicity study was run to determine if there are effects on human spermatogenesis. No abnormality in testicular function tests was observed; however, this study was performed at doses less than those to be used in this study. Due to the effect on embryo-fetal development seen in animals, and the presence of favipiravir in semen for several days after the end of therapy, the recommendation is for male and female contraception for seven days following the end of treatment, in the dose regimen for influenza. Details of the reproductive toxicity studies may be found in the Investigator's Brochure.

Favipiravir is both metabolized by, and inhibits, aldehyde oxidase (AO). A potential interaction exists between favipiravir and drugs oxidatively metabolized by the AO pathway, where blood concentration of these drugs or favipiravir may be increased. Similarly, a potential interaction exists between favipiravir and drugs inhibiting AO activity, where blood concentration of favipiravir may be increased. Similarly, a potential interaction exists between favipiravir and drugs inhibiting AO activity, where blood concentration of favipiravir may be increased. Favipiravir should not be used with pyrazinamide.

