6.7 Prohibited Concomitant Therapy

The following may interact with favipiravir and risks and benefits should be carefully considered prior to treatment with the following:

- Any other anti-viral medication whether investigational or approved.
- Any drugs known to significantly inhibit AO activity (e.g., pyrazinamide, amitriptyline, chlorpromazine, clomipramine, clozapine, erythromycin, ketoconazole, nortriptyline,

quetiapine, raloxifene, perphenazine, promethazine, propafenone, tamoxifen, thioridazine).

- Any drugs metabolized by the AO pathway (e.g., famciclovir, hydralazine, lamivudine, sulindac, zaleplon, ziprasidone).
- Drugs with possible drug-drug interactions (concomitant medications requiring particular attention see the Investigator Brochure).

For hospitalized subjects on the favipiravir + SOC arm, site staff will be reminded to consider the above prior to prescribing concomitant medications.

The following message appears on the Diary Card given to subjects that are discharged with favipiravir to take at home (see Section 6.3.1):

Favipiravir can slightly increase the concentration of acetaminophen (Tylenol) in the blood. Do not take more than 3000 mg (do not forget to include any acetaminophen that could be in over-the-counter preparations) in a 24-hour period as long as you are taking favipiravir.

There are possible interactions of favipiravir with other drugs. During the time that you remain on favipiravir, do not take any medications or supplements that you were not taking while you were in the hospital, without getting approval first from the study doctor.

Favipiravir can cause you to be mildly sensitive to sunlight. Please avoid excessive exposure to sunlight or artificial ultraviolet light (tanning machines) while you are on favipiravir.

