7.1 Day 1 (PRE-DOSE)

- Obtain informed consent.
- Verify eligibility per the inclusion and exclusion criteria. (See Sections 5.1 and 5.2)
 - o Review and record medical history, including tobacco use, to ensure there are no exclusionary illnesses.
 - Review and record concomitant medications for possible prohibited medications. (See Section 6.7)
- If subject is female of child-bearing potential and meets inclusion criteria 4.c, obtain urine or blood pregnancy test and proceed it result is negative.
- Measure and record vital signs (BP, HR, Temp, Resp).
 - **NOTE:** vital signs to be recorded and entered in the EDC every day while subject is in the hospital and on return study visits after discharge.
- Perform Physical exam (may be done by the Principal Investigator or their designee)
- Assess and record baseline clinical status according to the following study-specific 6-point scale:
 - 1. Not hospitalized
 - 2. Hospitalized, not requiring supplemental oxygen
 - 3. Hospitalized, requiring supplemental oxygen
 - 4. Hospitalized, on non-invasive ventilation or high flow oxygen devices
 - 5. Hospitalized, on invasive mechanical ventilation or ECMO

6. Death

NOTE: Clinical Status to be recorded and entered in the EDC every day while subject is in the hospital and on return study visits after discharge.

- Assess and record NEWS2 (See charts by clicking this link: https://www.rcplondon.ac.uk/projects/outputs/national-early-warning-score-news-2
 - **NOTE:** NEWS2 assessment to be recorded and entered in the EDC every day while subject is in the hospital and on return study visits after discharge.
- Assess and record ECOG Performance Status and Study-specific Symptom Status (see Appendix A).
 - **NOTE:** ECOG Performance Status and Study-specific Symptom Status to be collected and recorded every day while the subject is in the hospital and on return study visits after discharge.
- Collect nasopharyngeal and oropharyngeal swabs for virologic testing. (See Virology Laboratory Manual.)
- Collect blood samples for:
 - o Antibodies to SARS-CoV-2.
 - o Hematology and clinical chemistry laboratory analyses
- Collect and record SpO2 by Finger Sensor
 - **NOTE:** SpO2 to be recorded and entered in the EDC every day while subject is in the hospital and on return study visits after discharge.
- Perform subject randomization (via EDC) to establish treatment arm (favipiravir + SOC or SOC alone).

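### The protocol's rule against giving favipiravir with pyrazinamide is weakened to a risk-benefit consideration in Section 6.7, the section sites are told to check

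*Protocol*

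**What the plan says.** Protocol Section 2.2 describes interactions through aldehyde oxidase (AO) in general terms: drugs that inhibit the enzyme may raise favipiravir concentrations, and drugs cleared by it may themselves accumulate. It then singles out one drug: "Favipiravir should not be used with pyrazinamide". No other drug is named there.

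Protocol Section 6.7 is headed Prohibited Concomitant Therapy. Its lead-in says that "risks and benefits should be carefully considered prior to treatment with the following". Two of the bullets beneath it name drugs:

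- Inhibitors: "Any drugs known to significantly inhibit AO activity (e.g., pyrazinamide, amitriptyline, chlorpromazine", followed by 12 more names.
- Drugs cleared by the enzyme: "Any drugs metabolized by the AO pathway (e.g., famciclovir, hydralazine, lamivudine, sulindac, zaleplon, ziprasidone".

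A further bullet sends the reader elsewhere for other possible interactions: "concomitant medications requiring particular attention see the Investigator Brochure". For inpatients on the favipiravir arm, "site staff will be reminded to consider the above prior to prescribing concomitant medications".

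Protocol Section 7.1 opens its eligibility step with "Verify eligibility per the inclusion and exclusion criteria. (See Sections 5.1 and 5.2" and places beneath it the instruction "Review and record concomitant medications for possible prohibited medications. (See Section 6.7".

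**The concern.** Section 2.2 gives a rule for one drug, but it is a background section. Section 6.7 is the section staff are told to use, and it treats that drug no differently from the other 20 it lists for AO interactions. Advising against a combination and asking for its risks and benefits to be weighed are different instructions, even if the former is read only as strong advice.

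The ambiguity has a practical effect at two points. At entry, the medication check sits under eligibility verification and points to Section 6.7, so the answer depends on whether staff follow the heading or the sentence under it. During dosing, hospital staff are only reminded to consider the list. What is at stake is subject safety: by the sponsor's own account, AO inhibitors may raise favipiravir concentrations, and pyrazinamide is the one drug it ruled out.

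**Working it through.** There is no planned figure to reproduce. The check is a count of the drugs named and a comparison of the sections.

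**Count of drugs named in the two AO bullets of Protocol 6.7**

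- AO inhibitors: pyrazinamide, amitriptyline, chlorpromazine, clomipramine, clozapine, erythromycin, ketoconazole, nortriptyline, quetiapine, raloxifene, perphenazine, promethazine, propafenone, tamoxifen, thioridazine = 15.
- Drugs metabolized by AO: famciclovir, hydralazine, lamivudine, sulindac, zaleplon, ziprasidone = 6.
- No name appears twice, so 15 + 6 = 21 distinct drugs, and 21 − 1 = 20 besides pyrazinamide.

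Acetaminophen also appears in Section 6.7, but only in the Diary Card text and with its own daily limit, so it is not counted.

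**What each text bars among the 21**

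| Text | Drugs barred |
|---|---|
| Section 2.2 | 1 (pyrazinamide) |
| Section 6.7, heading read literally | 21 |
| Section 6.7, lead-in sentence | 0 |

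Neither reading of Section 6.7 reproduces the rule in Section 2.2. The heading goes further than that rule and the sentence falls short of it.

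**Whether another section carries the rule**

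- Exclusion criteria (Protocol 5.2 and synopsis): pyrazinamide is not named. The nearest criterion, number 12, covers other antivirals and participation in other COVID-19 trials. Antivirals fall under the same soft sentence in Section 6.7 but are backed by that exclusion; pyrazinamide has no such support.
- Exclusion 1 (bacterial respiratory infection) may keep out some users, but the documents do not say what pyrazinamide is used to treat.
- Stopping rules (Protocol 5.4): these act on liver tests and uric acid, so only after exposure. Among the protocol's chemistry days (1, 3, 8, 11, 15, 29), those after baseline and within the 14 dosing days are 3, 8 and 11. The first therefore follows the Day 1 loading doses.
- Diary Card (Protocol 6.7): it stops discharged subjects from starting new drugs without approval. It does not name pyrazinamide, and a drug already taken in hospital would pass.
- SAP: pyrazinamide is not mentioned.

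In the text available, pyrazinamide is named only in Protocol 2.2 and 6.7.

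**Subjects affected**

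About 50 subjects randomized 1:1 gives 50 / 2 = 25 planned for favipiravir. The documents give no rate of pyrazinamide use and no size of harm, so no expected number exposed or harmed can be calculated.

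**The case against.** The strongest reply is that the two sections can both be obeyed. Pyrazinamide comes first in a list headed as prohibited, Section 7.1 calls that list prohibited, and nothing in Section 6.7 allows the drug. A site that withholds it complies with Sections 2.2, 6.7 and 7.1 together. Under the heading reading, Section 6.7 is broader than Section 2.2 and not softer. This stands: the defect is ambiguity, not permission.

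The second reply is that other controls exist. Exclusion 14 lets the investigator refuse any subject, concomitant medications are reviewed on Days 2, 3, 8, 11 and 14 and throughout hospitalization, and the Diary Card restricts new drugs after discharge. The Investigator Brochure may also state the rule, but it is not available here. These controls reduce the risk. None of those that can be read states the rule, and none requires a drug already in use to be stopped. A ban in the Brochure would not remove the inconsistency within the protocol.

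The third reply is that the count of 21 is not a measure of harm. The names are only examples, and two further bullets in Section 6.7 cover other antivirals and drugs listed in the Brochure. That is right. The count shows that the texts disagree and says nothing about how many subjects are affected.

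The last reply is that one added line leaves the mismatch between heading and sentence in place for the other 20 drugs. That is also true, but it is a separate matter. For those drugs Section 2.2 sets no specific rule that Section 6.7 could weaken.

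**Conclusion.** The concern holds. Section 2.2 rules out pyrazinamide without qualification, while the operative sentence of Section 6.7 places it under risk-benefit judgement. Section 7.1 sends the eligibility check to Section 6.7 and not to Section 2.2. Following the 6.7 sentence as written could allow a combination the sponsor rules out.

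The point is minor. It concerns safety wording for about 25 planned favipiravir subjects and leaves the sample size, endpoints and analyses untouched. Confidence is high on the inconsistency, which can be read directly from the text. It does not extend to any consequence: that pyrazinamide use would be rare in this population is an assumption without a source in the documents. The conclusion does not rest on it, because the correction is worth making at any rate of use.

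**What to change.** In Protocol 6.7, add a separate line stating that pyrazinamide must not be given with favipiravir, and take it out of the list of examples. Leave the other 14 named AO inhibitors and the 6 drugs metabolized by AO under risk-benefit judgement. The existing Section 7.1 check then applies the rule at entry, and the Section 6.7 reminder carries it through dosing. A matching exclusion criterion in Section 5.2 and the synopsis is optional.

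The cost is one line of text. No visit, sample size or analysis changes. The one downside is that the Section 7.1 check comes before randomization, so a subject on pyrazinamide might be excluded whichever arm would have been assigned.

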2.3 Clinical Experience

Overall, more than 40 clinical studies with favipiravir have been conducted globally, mainly in the US and Japan. Recently, China has begun studying favipiravir in patients with severe influenza as well as COVID-19. More than 3100 study subjects have received at least one dose of favipiravir manufactured by Toyama Chemical. Favipiravir has been well tolerated in studies

in adults and elderly subjects with uncomplicated influenza. A consistent safety profile composed of relatively low frequencies of mild to moderate adverse events (AEs) clustering around the system organ classes of gastrointestinal disorders, investigations, and infections and infestations has been characterized. Mild to moderate transient, asymptomatic elevations in serum uric acid and mild to moderate diarrhea are the two most common AEs known to occur with favipiravir. In double blind studies, the adverse event profile of favipiravir and placebo were similar with the exception of elevations of uric acid. Details can be found in the Investigator's Brochure.

Favipiravir has been used in an open label study in patients with Ebola, (2400 mg twice eight hours apart, followed by 1200 mg 8 hours later and then 1200 mg BID for the following 9-13 days). Although conclusions about efficacy cannot be reached because of the lack of a concurrent control group, favipiravir at this regimen appeared to be well tolerated. A study in Japan in patients with Severe Fever with Thrombocytopenia administered 1800 mg BID Day 1 followed by 800 mg BID for the next 13 days. It has also been used under compassionate use in patients with rabies or other unusual RNA virus illnesses.

2.5 Phase 1 Study Steady State Exposure

[figure not shown]
In a Phase 1 study in Japan, steady state exposures above the influenza target were achieved, which should cover the necessary exposure for SARS-CoV-2.

Similar to the PK profile above, the studies in the global influenza program using 5-days of treatment, demonstrated a similar PK profile, albeit with lower exposures. Below is the graph from US316, one of the US pivotal trials, a five-day study of 1800 mg BID Day 1 followed by 800 mg BID Days 5. As can be seen, the mean daily trough levels were above the target level of 20 ug/ml.

Below is the same graph for US317, the second pivotal trial in the program.

2.6 Rationale for 14-day Dosing Regimen

A Chinese study reported that patients in the control group (Ketruda plus aerosolized interferon) shed virus for a mean of 11 days, and the mean time to clearance in the group on favipiravir plus interferon was four days. Therefore, a mean time treatment duration of 14 days was chosen, in case interferon plus favipiravir was more effective than favipiravir alone, given the safety data supporting treatment of 10 days and beyond.

• (https://www.sciencedirect.com/science/article/pii/S2095809920300631)

